9.3.2. Secondary Efficacy Estimands

All secondary endpoints defined in Section 3 will be considered on the ITT population.

Intercurrent events strategies will be dependent on whether the endpoint is one evaluating the Objective 1 (to evaluate the effect of EDP1815 on the development and severity of complications of COVID-19 infection) or Objective 2 (To evaluate the effect of EDP1815 on length of hospitalization and recovery in participants with COVID-19) as follows:

Table 7: Intercurrent Event Strategies for the Secondary Estimands

Intercurrent event	Strategy for endpoints relating to Objective 1	Strategy for endpoints relating to Objective 2
Treatment discontinuation before the end of the 11 day treatment period	Treatment policy Actual values will be used regardless of treatment discontinuation	
Death prior to time of endpoint evaluation	Composite Subjects who die will be given a worst-case value from time of death	Competing risk Deaths will be accounted as a competing risk
Discharge prior to time of endpoint evaluation	While on treatment ¹ Values up to the time of discharge will be used. Treatment policy ² Actual values will be used regardless of inpatient/outpatient status	Treatment policy Actual values will be used regardless of inpatient/outpatient status
Initiating other experimental treatment not considered standard of care before endpoint evaluation	While-on-treatment Values prior to starting experimental treatment will be used	

¹ This will be used for all endpoints which are not recorded after discharge (e.g. S/F ratio).

² This will be used for all endpoints which are recorded after discharge (e.g. those relating to the WHO OSCI scale).

Population level summary measure will be assigned as appropriate to the type of endpoint as follows:

Table 8: Population Level Summary Measures for the Secondary Estimands

Type of endpoint	Population level summary measures
Categorical endpoint	Summary statistics, p-value for treatment difference (CMH test)
Binary endpoint	Risk difference between EDP1815 and placebo
Continuous endpoint	Mean difference between EDP1815 and placebo
Number of days with an event	Summary statistics
Time to event	Hazard ratio for EDP1815 vs. placebo

Full details of the individual secondary efficacy estimands will be provided in the SAP.

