The difference in proportions between the treatment groups in the percentage of participants remaining at or below their baseline WHO OSCI score will be reported together with the corresponding 95% confidence interval at Days 4, 7, 10, 14, 21 and 42.

A CMH test for ordinal data will be used to compare the treatment groups with respect to the maximum WHO OSCI score recorded by each participant. Within each maximum score, the time in days spent at that score will also be summarised.

Overall survival will be analysed using a Cox proportional hazards (Cox-PH) model. The model will include parameters for treatment together with the additional baseline covariates which were identified during the blinded review of the overall survival model. Participants who are still alive at the end of the 42-day study period or who withdraw prematurely from the study for reasons other than death will be censored on the day of their study completion/withdrawal. The hazard ratio for treatment difference with corresponding 95% confidence interval will be presented.

If during the course of the study, a newly approved medication for COVID-19 becomes part of the standard of care treatment at the investigational site, a further sensitivity analysis will be performed. A time-dependent covariate for use of the new medication (yes, no) will be included in the model described above together with its interaction with treatment.

Intubation and mechanical ventilation free survival will be analysed in the same manner as described for overall survival above.

Number of days requiring oxygen therapy, number of days with pyrexia, maximum daily temperature, minimum and maximum SpO₂ values will be summarised only.

Time to discharge will be analyzed using the Fine and Gray subdistributional hazards model to allow for the competing risk of death (Fine 1999). The model will include parameters for treatment together with the additional baseline covariates which were identified during the blinded review of the time to discharge model.

Subjects who are not discharged and are still alive at the end of the 42-day study period or those who withdraw prematurely from the study without being discharged or dying will be censored on the day of study completion/withdrawal.

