9.3.3 WHO OSCI Score

9.3.3.1 Estimands

The endpoints will be recorded (inpatients) or derived (outpatients) WHO OSCI score at Days 4, 7, 14, 21 and 42. Population summary methods will be:

- Percentage of participants at each level of the WHO OSCI score
- Percentage of participants with each possible shift from Baseline in WHO OSCI score
- Percentage of participants remaining at their baseline WHO OSCI score (or lower)

- Percentage of participants reporting each level of WHO OSCi score at their worst post-baseline day

The intercurrent event strategy for these estimands is described in [Table 11](#).

Table 11 Intercurrent Event Strategies for the WHO OSCi Score Secondary Estimands

Intercurrent event	Strategy to account for intercurrent event
Death prior to the study day of interest	Composite WHO OSCi score of 8 will be carried forward to all further study days
Discharge prior to the study day of interest	Treatment policy The WHO OSCi score will be derived from the participant daily diary using the rules in Section 5.3.3.4
Treatment discontinuation before the study day of interest and no other experimental treatment not considered standard of care initiated	Treatment policy WHO OSCi score used as recorded for inpatients or derived for outpatients from the participant daily diary using the rules in Section 5.3.3.4
Withdrawal from the study due to initiating other experimental treatment not considered standard of care before the study day of interest	While-on-treatment Participants will be excluded from the analysis at that study day

Data missing for reasons other than an intercurrent event as detailed above will not be imputed.

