9.3.3.2 Analytical Approach

WHO OSCi score at Baseline and Days 4, 7, 14, 21 and 42 will be summarized as a categorical variable. A Cochran-Mantel Haenszel (CMH) test for ordinal data will be used to compare the groups with respect to the percentage of participants reporting each category in the scale at each visit. Histograms of WHO OSCi scores at Days 4, 7, 14, 21 and 42 will also be produced.

Shift tables showing the changes from Baseline at each of Days 4, 7, 14, 21 and 42 in WHO OSCi score will also be provided.

The proportion of participants remaining at or below their baseline WHO OSCi score will be reported at Days 4, 7, 10, 14, 21 and 42 together with the corresponding 95% exact confidence interval. These proportions and confidence intervals will also be displayed graphically.

The maximum WHO OSCi score reported by each participant during the study will also be summarized and compared between the treatment groups with a CMH test for ordinal data. Within each maximum score, the number of days spent at that score will also be summarized. A histogram of maximum WHO OSCi score will also be produced.

WHO OSCI scores at all study days will also be listed.

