CDISC standards will not be used for this study. The analysis datasets will be produced using a similar structure to those described for the analysis dataset model (ADaM) but will be not be fully validated and will be programmed directly from the source CRF and external data rather than from SDTM datasets.

All analyses will be performed using SAS version 9.2 or higher (SAS Institute, Cary, NC, USA).

14 Summary of Changes to the Protocol

Not applicable.

15 References

Fine, J. a. (1999). A Proportional Hazards Model for the Subdistribution of a Competing Risk. *Journal of American Statistics Association*, 94(446), 496-509.

16 Appendix 1: List of Tables, Figures and Listings

All outputs detailed in the following sections will be produced for the final analysis. Programming notes also indicate where tables will be produced for interims using the following abbreviations:

DMC-Blinded – produced as a blinded output with only the overall column shown - all DMC meetings

DMC-Unblinded – produced as an unblinded output – all DMC meetings

DMC-Safety – produced as an unblinded output – all DMC meetings after participants aged >65 years have been approved for inclusion

DMC-Efficacy – produced as an unblinded output – DMC meeting after 60 participants have completed 21 days treatment only

Note that some outputs will only be produced if the criterion specified in the programming notes is met.

Highlighted **XXXXX** text indicates that the full title is dependent on currently unknown factors (e.g. name of medications which becomes SOC during the study).

If the study is stopped early, outputs will be produced as specified in Early Stop column.

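### The SAP drops the protocol's between-arm risk difference and 95% CI for remaining at or below baseline OSCI, leaving only per-arm proportions with their own intervals

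*SAP*

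**What the plan says.** Protocol 9.4.1.2 addresses this endpoint by name. It reports "The difference in proportions between the treatment groups in the percentage of participants remaining at or below their baseline WHO OSCI score", and does so "together with the corresponding 95% confidence interval at Days 4, 7, 10, 14, 21 and 42". Protocol 9.3.2, Table 8, lists the population summary measure for a binary endpoint as "Risk difference between EDP1815 and placebo", and leaves full details of the secondary estimands to the SAP.

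SAP 9.3.3.1 gives the summary measure only as a percentage of participants, without a contrast between arms. SAP 9.3.3.2 reports the proportion meeting the endpoint on each of the same six study days, and the only interval it attaches to that proportion is worded "together with the corresponding 95% exact confidence interval". It then has those proportions and intervals plotted. SAP section 9 presents efficacy outputs by treatment group and overall. Section 14, headed "Summary of Changes to the Protocol", is marked as not applicable.

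**The concern.** The two documents specify different analyses of the same endpoint, and the SAP is the one programmers will follow. Under it, the protocol's between-arm interval is not produced, and the change is not declared.

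The natural substitute for a reader is to check whether the two per-arm intervals overlap. That is a conservative check: two 95% intervals can overlap while the 95% interval for the difference excludes zero.

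Two features of the trial make the difference useful even though it is a pilot. Both documents say the study is meant to evaluate endpoints for relevance and sensitivity and to inform later sample sizes, and a between-arm effect with its precision serves that directly. Table 14.2.4.3 and Figure 14.2.4.2 are also among the efficacy outputs for the DMC meeting at 60 participants. There, SAP 7.4.3 asks members to weigh an emerging treatment difference against its variability when advising on 40 more participants.

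**Working it through.** **Comparison of the texts**

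| Item | Protocol | SAP |
|---|---|---|
| Summary measure | Risk difference (Table 8) | Percentage of participants (9.3.3.1) |
| Quantity reported | Difference in proportions (9.4.1.2) | Proportion (9.3.3.2) |
| Interval | 95% CI for the difference | 95% exact CI for the proportion |
| Between-arm comparison | Yes | None stated |

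The SAP sentence does not itself say per arm. That reading follows from three things:
- SAP section 9 presents results by treatment group.
- The interval is attached grammatically to the proportion.
- Figure 14.2.4.2 is titled as a proportion with a 95% CI.

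The output list in SAP Appendix 1 agrees. Tables 14.2.4.1 (OSCI by day) and 14.2.4.4 (maximum OSCI) are labelled as summary and analysis, and their early-stop versions lose the inferential part. Table 14.2.4.3, for this endpoint, is labelled as a summary only and is kept unchanged on early stopping.

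**The plan's own figures.** Neither document gives a rate or precision figure for this endpoint. The only precision table concerns trough S/F ratio, and it reproduces: half-width = t(0.975, N−2) × SD × √(2/(N/2)). For N = 60 and SD = 100 this is 51.7, as stated, and all 18 entries of SAP Table 8 agree to one decimal. That table is framed as an interval for the treatment difference.

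**Illustration.** Inputs: 30 per arm (60 randomised 1:1). The event counts are assumptions.

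For 27/30 versus 20/30:
- Exact (Clopper-Pearson) interval for x of n: from the 2.5% quantile of Beta(x, n−x+1) to the 97.5% quantile of Beta(x+1, n−x). This gives 73.5–97.9% and 47.2–82.7%. They overlap between 73.5% and 82.7%.
- Difference d = 90.0 − 66.7 = 23.3 points.
- Newcombe interval, built from the Wilson limits (l, u) of each arm. The Wilson limits are 74.4–96.5% and 48.8–80.8%.
  - Lower: d − √[(p₁−l₁)² + (u₂−p₂)²] = 23.3 − √(15.6² + 14.1²) = 2.3.
  - Upper: d + √[(u₁−p₁)² + (p₂−l₂)²] = 23.3 + √(6.5² + 17.9²) = 42.4.

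Range of assumed counts:

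| Counts | Per-arm exact 95% CIs | Difference | Newcombe 95% CI | Wald 95% CI |
|---|---|---|---|---|
| 24 v 21 | 61.4–92.3; 50.6–85.3 | 10.0 | −11.8 to 30.7 | −11.8 to 31.8 |
| 24 v 18 | 61.4–92.3; 40.6–77.3 | 20.0 | −3.2 to 40.6 | −2.6 to 42.6 |
| 27 v 20 | 73.5–97.9; 47.2–82.7 | 23.3 | 2.3 to 42.4 | 3.3 to 43.3 |
| 28 v 21 | 77.9–99.2; 50.6–85.3 | 23.3 | 3.5 to 41.8 | 4.7 to 42.0 |

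The per-arm intervals overlap in all four rows. The interval for the difference excludes zero in the last two. With 20/30 in one arm, 27/30 in the other is enough for the Newcombe interval to exclude zero, but the exact per-arm intervals separate only from 29/30.

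**How often the two presentations disagree.** Each pair of counts at 30 per arm was weighted by its binomial probability under assumed true rates. The probabilities were summed over pairs where the per-arm intervals overlap but the Newcombe interval excludes zero:

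| True rates | Probability of disagreement |
|---|---|
| 70% v 70% | about 5% |
| 80% v 70% | about 13% |
| 90% v 80% | about 14% |
| 80% v 60% | about 31% |
| 90% v 67% | about 39% |

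**The case against.** The SAP does not withdraw the protocol's analysis. It states that it builds on the protocol, and it is merely silent on the difference. The point estimate is one subtraction away from the two reported proportions, so what is really missing is its interval. That narrows the loss to the interval, but the interval is the part that carries the uncertainty, and a programmer working from the SAP and its output list would not produce it.

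The arms are still compared on OSCI by CMH tests, on the score at each visit and on the maximum score. Under SAP 5.3.3.4 the binary endpoint requires that no earlier score exceeded baseline, so it is closely related to the maximum. These tests do limit the damage. They do not estimate the same quantity: a visit-day score ignores earlier worsening, the study-wide maximum is not tied to a particular day or to the participant's baseline, and the SAP attaches no effect size to either.

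The 27/30 versus 20/30 example is assumed and lies towards the unfavourable end. For smaller differences the two presentations usually lead to the same reading. That stands, and the tables above show the range.

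Finally, the trial is unpowered, every analysis is declared descriptive, and no formal rule depends on this interval. This bears on severity only. A risk difference with a confidence interval is itself descriptive, and the protocol asks for it on those terms.

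**Conclusion.** The concern holds. For this endpoint the SAP leaves out the protocol's summary measure and its interval, offers no other treatment comparison, and does not declare the change. The discrepancy is established by the text and needs no assumption beyond the per-arm reading, which the SAP's presentation rule and output titles support.

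The practical size depends on event rates the documents do not give. At 30 per arm and the true rates tried, overlap of per-arm intervals and the interval for the difference would disagree in about 5% to 39% of trials. The primary analysis is unaffected. This should be corrected, but it does not threaten the trial's main conclusion.

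**What to change.** - **SAP 9.3.3.1:** name the EDP1815-minus-placebo risk difference as the summary measure for this endpoint.
- **SAP 9.3.3.2 and Table 14.2.4.3:** report that difference with a 95% confidence interval at each study day, and state the method. Newcombe's interval or an exact one would suit these arm sizes; the protocol names none. Keep the per-arm proportions and exact intervals as description.
- **Early-stop entry for Table 14.2.4.3:** exclude the interval for the difference there, in line with SAP 9.1.1.1 and the neighbouring tables.
- **If the omission was intended:** record and justify it in SAP section 14 instead.

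While editing, settle Day 10. It is in the text for this endpoint in Protocol 9.4.1.2 and SAP 9.3.3.2, but not in the titles of Table 14.2.4.3 and Figure 14.2.4.2.

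The cost is one more column in an existing table and a few lines of SAP text. No new data are needed.

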9.3.4 Overall Survival and Intubation and Mechanical Ventilation Free Survival

9.3.4.1 Estimands

The endpoint will be time to event in days as defined in [Section 5.3.3.5](#). The population summary measure of interest will be the hazard ratio for the EDP1815 group compared to the placebo group.

The intercurrent event strategy for these estimands is described in [Table 12](#).

Table 12 Intercurrent Event Strategies for Overall Survival and Intubation and Mechanical Ventilation Free Survival Secondary Estimands

Intercurrent event	Strategy to account for intercurrent event
Discharge prior to Day 42	Treatment policy Participants actual status will be used
Treatment discontinuation before Day 14 without withdrawal from the study	Treatment policy Participants actual status will be used
Withdrawal from the study	While-on-treatment Participants will be censored at the time of withdrawal from the study.

For the interim analysis presented at the DMC meeting when 60 patients have completed 21 days in the study, subjects who are still ongoing and have not met the criteria for the relevant event will be censored at the date of the data cut.

9.3.4.2 Analytical Approach

The number of participants who died and the number of participants censored will be presented together with Kaplan-Meier estimates of median time to death (where calculable) and the predicted proportion of participants who died at Days 4, 7, 14, 21 and 42. Kaplan-Meier curves of overall survival will also be presented.

Overall survival will be analyzed using a Cox proportional hazards (Cox-PH) model. The model will include parameters for treatment together with the additional baseline covariates which were identified during the blinded review of the overall survival model. Participants who are still alive at the end of the 42-day study period or who withdraw prematurely from the study for reasons other than death will be censored on the day of their study completion/withdrawal. The hazard ratio for treatment difference with corresponding 95% confidence interval will be presented.

If during the study, a newly approved medication for COVID-19 becomes part of the standard of care treatment at the investigational site, a further sensitivity analysis will be performed. A time-dependent

covariate for use of the new medication (yes, no) will be included in the model described above together with its interaction with treatment.

Overall survival information will be also be listed including survival status and time to death or censoring.

Intubation and mechanical ventilation free survival will be analyzed in the same manner as overall survival.

9.3.5 Time to Discharge, Time to SpO₂ ≥94% on Room Air and Time to Recovery

9.3.5.1 Estimands

The endpoint will be time to event in days as defined in [Section 5.3.3.6](#). The population summary measure of interest will be the hazard ratio for the EDP1815 group compared to the placebo group.

The intercurrent event strategy for these estimands is described in [Table 13](#).

Table 13 Intercurrent Event Strategies for Time to Discharge, Time to SpO₂ ≥94% on Room Air and Time to Recovery Secondary Estimands

Intercurrent event	Strategy to account for intercurrent event		
	Time to Discharge	Time to SpO ₂ ≥94% on Room Air	Time to Recovery
Death prior to the event	Competing Event Death will be considered as a competing event and accounted for as such in the analysis		
Discharge prior to the event with oxygen for home use	N/A	While-on-treatment Participant will be censored on the date of discharge	Treatment policy Actual values will be used regardless of inpatient/outpatient status
Discharged prior to the event without oxygen for home use	N/A	Composite Participant will be considered as having had the event on the date of discharge	Treatment policy Actual values will be used regardless of inpatient/outpatient status
Treatment discontinuation before the study day of interest without withdrawal from the study	Treatment policy Actual values will be used regardless of inpatient/outpatient status		
Withdrawal from the study for any reason	While-on-treatment Participant will be censored on the date of study withdrawal		

For the interim analysis presented at the DMC meeting when 60 patients have completed 21 days in the study, subjects who are still ongoing and have not met the criteria for the relevant event will be censored at the date of the data cut.

9.3.5.2 Analytical Approach

Time to discharge will be analyzed using a Fine and Gray subdistributional hazards model to allow for the competing risk of death (Fine, 1999). The model will include a parameter for treatment together with any additional baseline covariates identified during the blinded review of the time to discharge model.

The number and percentage of participants who are discharged, who die and who are censored will be reported together the estimate of median time to the event, and the predicted proportion of participants who were discharged at Days 4, 7, 14, 21 and 42. The estimated subdistributional hazard ratio (with 95% confidence interval) for treatment difference in risk of recovery and its p-value from the model will also be presented. Cumulative incidence functions for time to full recovery will also be plotted by treatment group.

Time to discharge information will be listed including event status and time to event/censoring or death.

Time to SpO₂ ≥94% on room and time to recovery will be analyzed in the same manner as described above for time to discharge.

9.3.6 Other Secondary Endpoints

Number and percentage of days requiring oxygen therapy and the sensitivity variable described in [Section 0](#) will be summarized for days 1-14, 1-28 and 1-42 and listed. Details of all oxygen therapy used will also be listed.

Number and percentage of days with pyrexia ≥ 38°C and the sensitivity variable described in [Section 5.3.3.8](#) will be summarized for days 1-14, 1-28 and 1-42 and listed. Maximum temperature for each participant will also be summarized. Daily temperature data will also be listed.

Minimum and maximum SpO₂ for each participant will be summarized and listed. Daily SpO₂ values will be included in the listing of daily S/F ratio data.

9.4 Exploratory Efficacy Analyses

9.4.1 Biomarkers

[Table 16](#) shows the parameters which will be collected and the units in which they will be supplied.

Actual values and change from baseline in cytokine levels will be summarized at Days 4 and 7. All cytokine level data will also be listed.

Actual values and change from baseline in inflammatory response markers will be summarized at Days 4 and 7. All inflammatory response marker data will also be listed.

